Statistical And Analytic Plan	
 • It is assumed that 50% of subjects will fail the baseline screening PSG. Thus, 318 subjects will be recruited initially. • 159 eligible subjects will be randomized in a 2:1 fashion to NCS vs. placebo, respectively; the initial group sizes will therefore be 106 NCS vs. 53 placebo subjects. The 2:1 randomization ratio is to allow for further randomization during the follow-up phase of the study. Based on our past studies we will assume a drop-out rate of 5% at 3 months. Therefore, the available sample size for analysis for Aim 1 will be 100 NCS vs. 50 placebo subjects. • All analyses will be conducted with Stata 13.0, with two-sided tests of hypotheses and a p-value < 0.05 as the criterion for statistical significance. • Analyses will be conducted according to the intent to treat principle, with subjects analyzed according to their initial treatment assignment. • Descriptive analyses will include computation of means (with 95% confidence intervals), standard deviations, medians, interquartile-ranges (IQR) of continuous variables and tabulation of categorical variables. • A two-group t-test for independent samples or Wilcoxon rank sum test will be used to test the primary hypothesis that

the changes in AHI are equal between the two treatment groups.

[figure not shown]
DATA AND SAFETY MONITORING PLAN

Participants' data will be closely monitored by an external Data Safety Monitoring Board (DSMB) and an external safety officer. They will monitor adverse events and treatment failures.

TABLE 1: SCHEDULE OF STUDY PROCEDURES

Percutaneous skin allergy test		X												
Blood tests		X			X									X
Ophthalmology exam		X			X									X
Nasal secretion testing		X			X									X
DXA scan		X			X									X
Urine pregnancy test		X			X									X
Randomization		X			X									
Dispense Study Drug		X			X									
Drug Compliance					X		X				X			X
Adverse Event Assessment		X	X	X	X	X	X	X	X	X	X	X	X	X

FIGURE 1: STUDY DIAGRAM

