4.8.1 Early Termination Study Visit

Subjects who withdraw from the study will have all procedures enumerated for Visit 5 at the early termination visit.

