6.3.2 Efficacy Analysis

The primary analysis will be based on an intention to treat approach and will include all subjects randomized at Visit 1.

The primary efficacy endpoint will be the change in AHI between Randomization and Visit 2.

Secondary endpoints will include the change in AHI at the 12-month visit in each group and the change in knee height, bone health, adrenal suppression, ocular health and infection at 12 months.

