6.4 Sample Size and Power

Sample size for primary endpoint:

All sample size calculations were conducted using nQuery Advisor software. It is assumed that 50% of subjects will fail the baseline screening PSG. Thus, 318 subjects will be recruited initially. 159 eligible subjects will be randomized in a 2:1 fashion to NCS *vs* placebo, respectively; the initial group sizes will therefore be 106 NCS *vs* 53 placebo subjects. The 2:1 randomization ratio is to allow for further randomization for Aim 3. Based on our past studies (see *Preliminary Data*), we will assume a drop-out rate of 5% at 3-months. Therefore, the available sample size for the primary endpoint analysis will be 100 NCS *vs* 50 placebo subjects. This is powered on a comparison of mean changes in AHI between NCS *vs* control subjects at 3-months, based on two prior studies (13, 15). The effect-size for the difference in mean changes between treatment groups for the Brouillette study, calculated as the absolute value of the difference in group means, divided by the pooled estimate of the SD of changes, was 0.87 (15), and for the Kheirandish-Gozal study was 1.75.(13) A two group t-test with a 0.050 two-sided significance level will have $\geq 99\%$ power to detect the effect size of 0.865 (observed in (13)) when the sample sizes in the two groups are 100 and 50, respectively. In addition, the two group t-test will also have $>99\%$ power to detect the effect size of 1.75 that was observed in (15). We will therefore have excellent power to determine treatment group differences of the magnitude observed by these past studies. However, as the effect sizes were so different for these two studies, and as the current study will include a more heterogeneous population, e.g., children with more severe OSAS, the observed effect-size may be smaller. If so, we will have 81% power to detect an effect size of 0.50. An effect-size of 0.50 corresponds to a mean reduction in AHI of 4.2/hr in the NCS group and no change in the placebo group, assuming the SD of changes is 8.4 (as observed in (13)); and an AHI reduction of 1/hr with NCS (and no change in placebo) if the SD of change is 2 as observed in (15). Any smaller difference between groups with respect to changes in AHI would not be clinically meaningful. We are therefore well-powered to detect meaningful changes for the primary endpoint.

Sample size for secondary endpoints:

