Comparison of the changes in AHI at 12 months: For this endpoint, the 100 remaining NCS subjects (assuming there were ~6 dropouts) at 3-months will be re-randomized in equal numbers to continued NCS or placebo. Assuming a conservative drop-out rate of 10%, there will be 45 evaluable subjects per treatment group at 12 months. We anticipate that subjects treated with NCS will continue to improve (i.e., have continued reductions in AHI), while those on placebo will have a worsening of their condition (i.e., increases in AHI). We anticipate that subjects who continue on NCS will have similar (or greater) improvements during the additional 9 months of follow-up as were observed during the first 3 months of treatment. Assuming that NCS subjects have a mean reduction in AHI of 4/hr, while placebo subjects have a mean increase of 3/hr, a two-sample t-test will have 97% power to detect this difference, assuming that the common SD of changes is 8.4 (as in (15)); if the SD of changes is 2.0 (as in (13)), then we will have >99% power. However, if the observed differences of the current study are smaller, a sample size of 45 in each group will have 80% power to detect an effect size of 0.597; this would be observed if the mean reduction in AHI is 2.4/hr for subjects treated with NCS, *vs* no change for subjects treated with placebo, assuming a SD of 4.0(13).

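### The plan has no missing-data rule, no analysis set for the second randomization and no stated use for the early-termination sleep study, so relapse-related exits could shrink the 12-month AHI contrast

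*Combined protocol and SAP*

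**What the plan says.** **Analysis set.** Section 6.3.2 describes the primary analysis as intention to treat and says that it "will include all subjects randomized at Visit 1". The synopsis (Statistical And Analytic Plan) adds that children are analysed by the treatment first assigned. No analysis set is given for the children re-randomized at 3 months.

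**Test and endpoints.** The synopsis names a two-group t-test or Wilcoxon rank sum test on change in AHI. Sections 6.1 and 6.2 tie the endpoints to the 3-month and 12-month visits.

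**Numbers.** In the synopsis, "the initial group sizes will therefore be 106 NCS vs. 53 placebo subjects", and with 5% loss "the available sample size for analysis for Aim 1 will be 100 NCS vs. 50 placebo subjects". Section 6.4 repeats this for the primary endpoint. For the 12-month comparison, where 100 NCS children are re-randomized equally, section 6.4 states: "Assuming a conservative drop-out rate of 10%, there will be 45 evaluable subjects per treatment group at 12 months". Section 3.3.2 gives different evaluable counts, 159 at 3 months and 100 at 12 months.

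**Children who leave.** Section 4.8.1: "Subjects who withdraw from the study will have all procedures enumerated for Visit 5 at the early termination visit". Section 4.4.2 lists a sleep study among the Visit 5 procedures. Section 8.11.1 says that treatment failures should be kept in the study where possible, whether or not they receive clinical treatment. It expects few, citing 9 of 464 (1.9%) in an earlier trial.

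**The concern.** A t-test or rank-sum test on change needs a follow-up AHI, so as named it leaves out any child without one. No imputation, model or sensitivity analysis is given to connect that test with the statement that all randomized children are included.

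The second randomization has a further gap. Both of its arms began on NCS, so analysis by the treatment first assigned cannot tell them apart.

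The 12-month comparison bears on the hypothesis that NCS needs ongoing maintenance. Section 6.4 expects AHI to rise in children switched to placebo, and section 4.8 allows withdrawal for safety. If children who relapse leave and are not counted, the placebo-switch arm looks better than it is and the benefit of continuing is understated. A sleep study is scheduled for those who withdraw, but the plan does not say whether it counts.

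**Working it through.** **1. The plan's own figures.** Dropout: 106 × 0.95 = 100.7; 53 × 0.95 = 50.35; 100 × 0.90 / 2 = 45. Power for a two-sided 0.05 two-sample t-test, from the noncentral t distribution:

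- 100 vs 50, effect size 0.50: 81.8% (stated 81%).
- 45 vs 45, 7/8.4 = 0.833: 97.4% (stated 97%).
- 45 vs 45, effect size 0.597: 80.0% (stated 80%).

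All reproduce.

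**2. Is the issue precision or bias?** If every randomized child supplied a value and the effect were unchanged, power would be 84.0% at 3 months (106 vs 53, 0.50). At 12 months (50 vs 50) it would be 84.0% for 0.597 and 98.5% for 7/hr with SD 8.4. The gain in precision is small, so what matters is bias.

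**3. Bias at 12 months by formula.** From section 6.4: mean changes of −4/hr (NCS) and +3/hr (placebo), SD 8.4, 10% loss; or a 2.4/hr difference with SD 4.0. Assumed, because the documents do not say who leaves: changes are normal, NCS exits are random, and placebo-switch exits are drawn at random from the worst fraction w of that arm. The mean of that tail lies SD × φ(z)/w above the arm mean, where z cuts off the top w. The mean of those remaining therefore falls by

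bias = (0.1/0.9) × SD × φ(z)/w.

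| w | φ(z)/w | Bias, SD 8.4 | Placebo mean left (true +3) | Share of 7/hr | Bias, SD 4.0 | Share of 2.4/hr |
|---|---|---|---|---|---|---|
| 0.1 | 1.755 | 1.64 | 1.36 | 23% | 0.78 | 33% |
| 0.3 | 1.159 | 1.08 | 1.92 | 15% | 0.52 | 21% |
| 0.5 | 0.798 | 0.74 | 2.26 | 11% | 0.35 | 15% |

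**4. Other exit patterns.** 20,000 simulated trials of 50 vs 50, with a t-test on the children remaining:

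| Exits | Difference (true 7, SD 8.4) | Power | Difference (true 2.4, SD 4.0) | Power |
|---|---|---|---|---|
| 5 random per arm | 7.0 | 97% | 2.4 | 80% |
| 1 worst placebo, 1 random NCS | 6.6 | 97.5% | 2.2 | 79% |
| 5 placebo, exit correlated 0.5 with AHI change; 5 random NCS | 6.2 | 94% | 2.0 | 67% |
| 5 worst placebo, 5 random NCS | 5.4 | 89% | 1.6 | 55% |
| All above one common AHI rise, 10% overall | 5.2 | 91% | 1.7 | 66% |
| 5 worst in each arm | 7.0 | 99% | 2.4 | 88% |
| 5 worst NCS, 5 random placebo | 8.6 | >99% | 3.2 | 97% |

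The common-rise pattern means exits of 3.5% NCS and 16.5% placebo in the first scenario, and 5.1% and 14.9% in the second. With SD 2.0 and a 7/hr difference, power stays above 99% in every pattern run.

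**5. The 3-month comparison.** With 5% loss the multiplier is 0.05/0.95. If the losses in one arm come from its worst 5% to worst half, the shift is 0.11 to 0.04 SD, against the effect size of 0.50. The plan gives no comparable reason to expect relapse-driven exit in the first three months.

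**The case against.** Several points on the other side stand.

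- A reader might take the 45 per group for an error. It is not: sizing on numbers after dropout is normal practice, and it does not define an analysis set.
- A reader might infer that the plan breaks an intention-to-treat commitment in both comparisons. The sentence in section 6.3.2 covers the primary analysis only; for the re-randomized children the plan is silent.
- A reader might infer that the early-termination sleep study will be discarded. The documents do not say so. Section 4.8.1 is compatible with using it as the final value; there is simply no stated use.
- A reader might infer that relapsing children will leave and that the difference will shrink. Section 8.11.1 aims to keep them and expects few, and the 10% loss is not tied to relapse. The 1.9% rate corresponds to about one child in an arm of 50, which takes 7.0 to 6.6/hr.

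The retention policy lowers the likely bias but does not close the gap. Section 6.4 still plans for 10% loss. A child who is kept in the study and treated clinically may have a 12-month AHI that hides the relapse, and no analysis rule covers that value.

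**Conclusion.** The concern holds as a gap in the analysis plan. The statement about all randomized children is not matched by a method that could deliver it; the second randomization has no analysis set; and neither the early-termination AHI nor an AHI after clinical treatment has a stated role.

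The consequence for the 12-month comparison is conditional. Under exits concentrated among relapsing placebo-switch children, with random NCS exits, the bias is about 0.7 to 1.6/hr of 7/hr (SD 8.4) or 0.35 to 0.8/hr of 2.4/hr (SD 4.0). The smaller-effect scenario is the more vulnerable: power falls from 80% to 55% if the five worst placebo-switch children leave. The bias is about 0.4/hr of 7/hr for one relapsing child, nil when exits are alike in both arms, and reversed when the worst NCS children leave. These sizes rest on normal changes and assumed exit patterns; the documents support none of the patterns in particular. The change should be made, because otherwise these choices are left until the data are in hand.

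**What to change.** 1. Define the analysis set for each randomization as all children randomized at that step, as assigned at that step.
2. Where the scheduled sleep study is missing, count the early-termination AHI as a follow-up value, with its actual time.
3. Analyse AHI with a baseline-adjusted, likelihood-based repeated-measures model using all available studies, with the month-3 AHI as baseline for the second randomization. Keep the t-test or rank-sum test on observed values as a sensitivity analysis.
4. Keep AHI measured after clinical treatment in the as-assigned analysis, in line with section 8.11.1. Add one sensitivity analysis using the last study before clinical treatment and one for informative dropout.
5. Reconcile section 3.3.2 (159 and 100 evaluable) with section 6.4 (150 and 90).

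The cost is SAP wording and some programming; no new procedure is needed. There are two limits. Early-termination values come from varying times. A child with no follow-up study, including one who never attends the early-termination visit, still adds almost nothing to the treatment contrast, so the model does not by itself make the analysis complete.

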Study Design	
 • Randomized, parallel, double-blind, placebo-controlled study.
Subject Population key criteria for Inclusion and Exclusion:	
Inclusion Criteria
 
 1. Subjects age 5-12 years. 2. Mild to moderate OSAS, defined as an obstructive apnea index (AI) of 1-20/hr of total sleep time (TST) or AHI 2-30/hr of TST. 3. Parent-related symptoms of habitual snoring (>3 nights per week). 4. No history of adenotonsillectomy or prior NCS use. 
Exclusion Criteria
 
 1. Severe OSAS or significant hypoxemia or hypercapnia on polysomnography (PSG), such that definitive treatment should not be delayed (AHI > 30/hr, more than 2% total sleep time with SpO₂ <90%, end-tidal PCO₂ > 60 mm Hg for \geq 5 minutes, pathologic arrhythmias). 2. History of recurrent throat infections 3. Any NCS use in the past 3 months, or NCS use for \geq 2 weeks in the past year 4. Abnormalities on baseline safety screening tests 5. Previous adenotonsillectomy 6. Previous adenoidectomy unless adenoidal tissue has been documented to have regrown 7. CPAP therapy 8. Pregnancy
Number Of Subjects	
 • 318 children will be recruited at CHOP. This is a single center study

Study Duration	
 • The participation of subjects randomized to the placebo group at the baseline visit will be 3 months. • The participation of subjects randomized to the NCS group at the baseline visit will be 12 months. • The entire study is expected to last 5 years
Study Phases	(1) Screening : screening for eligibility and obtaining consent and
Screening	(2) Intervention : Randomization: placebo or NCS for 3 months
Study Treatment	(3) Follow-up : randomization of NCS group to placebo or
Follow-Up	continuation of NCS for 9 months
Efficacy Evaluations	Change in AHI in the placebo and NCS groups at 3 months of therapy; and at 12 months of therapy
Pharmacokinetic Evaluations	N/A
Safety Evaluations	Worsening symptoms of OSAS, such as daytime sleepiness or development of complications, such as failure to thrive,

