6.2 Secondary Endpoints

Secondary endpoints will include the following:

- The change in AHI at the 3-month visit in each group according to the presence of atopy or obesity.
- The change in AHI at the 12-month visit in each group
- The change in knee height, bone health, adrenal suppression, ocular health and infection at 12 months.

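### The 12-month AHI change has no stated starting point in 6.2 or 6.3.2, 6.4 sizes it from month 3, and the planned unadjusted t-test leaves the Visit 2 AHI unused

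*Combined protocol and SAP*

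**What the plan says.** Section 6.3.2 fixes the primary change explicitly: from Randomization to Visit 2. For the later endpoint it says only "Secondary endpoints will include the change in AHI at the 12-month visit in each group". Section 6.2 has "The change in AHI at the 12-month visit in each group", directly after a 3-month subgroup endpoint phrased the same way. The Efficacy Evaluations row of the synopsis puts both times in one phrase: "Change in AHI in the placebo and NCS groups at 3 months of therapy; and at 12 months of therapy". None of the three names the visit from which the 12-month change is measured.

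Section 6.4 describes a particular window. The children still on NCS at month 3 are "re-randomized in equal numbers to continued NCS or placebo", and "there will be 45 evaluable subjects per treatment group at 12 months". Those who stay on NCS are expected to keep improving and "will have similar (or greater) improvements during the additional 9 months of follow-up as were observed during the first 3 months of treatment"; those switched to placebo are expected to worsen. The assumed means, a 4/hr fall and a 3/hr rise, are therefore most naturally month 3 to month 12 changes, although the power sentence does not say so. The planned test is a two-sample t-test, under the synopsis rule of "two-sided tests of hypotheses and a p-value < 0.05 as the criterion for statistical significance". No covariate is mentioned.

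**The concern.** The second randomization exists to show how long the NCS effect lasts (section 3.1.4), and it bears on the overall hypothesis that maintenance treatment is needed (section 1.1). For the switched-to-placebo arm, change from month 3 describes what happens after the drug is withdrawn. Change from baseline adds the earlier gain on drug to the later loss off drug, and can show little net change when AHI has risen since withdrawal. Both are legitimate summaries, but they answer different questions. With the reference unnamed, the choice could be made after the data are seen, and a reader of the results by group could not tell which question had been answered.

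There is also an efficiency point. Visit 2 AHI is measured just before the second randomization on every child who enters it. A t-test on change scores does not make the best use of that measurement.

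**Working it through.** **Inputs from section 6.4.** 45 evaluable per arm at 12 months; two-sided 0.05; main scenario -4/hr on continued NCS and +3/hr on placebo, common SD of change 8.4; fallback standardized effect size 0.597. For months 0 to 3: section 6.4 expects the later NCS gain to be similar to or greater than the earlier one, which puts the earlier fall at about 4/hr in the similar case; its primary-endpoint paragraph uses 4.2/hr (SD 8.4) or 1/hr (SD 2).

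**1. The plan's power.** Two-sample t-test, noncentrality = (difference/SD) / √(1/45 + 1/45), 88 degrees of freedom.
- Difference 4 + 3 = 7/hr, SD 8.4, effect size 0.833: 97.4% (plan: 97%).
- Effect size 0.597: 80.0% (plan: 80%).

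Both reproduce.

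**2. Moving the starting point.** Change from baseline = change in months 0 to 3 + change in months 3 to 12. All re-randomized children were on NCS in months 0 to 3, so the first term has the same expectation in both arms.

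| Fall in months 0–3 | Continued NCS, from baseline | Switched to placebo, from baseline | Arm difference |
|---|---|---|---|
| 1/hr | -5 | +2 | 7 |
| 3/hr | -7 | 0 | 7 |
| 4/hr | -8 | -1 | 7 |
| 4.2/hr | -8.2 | -1.2 | 7 |

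From month 3 the arm means are -4 and +3 in every row. The off-drug mean from baseline is 3 minus the 3-month fall, so it turns negative only when that fall exceeds 3/hr.

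**3. Precision from baseline.** The plan gives no SD for month 12 minus baseline. Taking the 7/hr difference over a range of assumed SDs:
- SD 8.4 (no increase): 97.4%
- SD 10: 90.7%
- SD 11: 84.7%
- SD 11.9 (8.4 × √2, independent increments): 78.9%

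Any loss depends wholly on the unknown SD.

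**4. Adjusting for Visit 2 AHI.** Assume equal variance σ² at months 3 and 12, and correlation r.
- SD of the change score: σ√(2(1 − r)).
- Residual SD with Visit 2 AHI as covariate: σ√(1 − r²).
- Ratio of the second to the first: √((1 + r)/2).

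Dividing 0.597 by this ratio gives the effective effect size:

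| r (assumed) | Ratio | 0.597 / ratio | Power, 45 per arm |
|---|---|---|---|
| 0.4 | 0.837 | 0.714 | 92% |
| 0.6 | 0.894 | 0.667 | 88% |
| 0.8 | 0.949 | 0.629 | 84% |

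**The case against.** The strongest reply is that 6.2 and 6.3.2 are silent rather than contradictory, and that 6.4 supplies the missing window in a paragraph headed as the 12-month comparison. That is a fair reading. A reader might infer two conflicting definitions, but the documents do not state two: the baseline reading rests on parallel wording alone. What remains is that the sections defining the endpoint leave its reference open, and the only section that implies one is the sample-size justification.

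Four stronger inferences are also unsupported.
- *The treatment comparison is distorted.* It is not. Both arms share months 0 to 3, so the expected difference is 7/hr either way.
- *The stated power is wrong, or holds only from month 3.* The figures reproduce, and power at a fixed standardized effect size with 45 per arm is the same for any change variable. Only the SD, and hence the effect size that a given AHI difference represents, could differ.
- *The off-drug result would switch between significant and non-significant.* The plan specifies no within-arm test.
- *The knee height, bone, adrenal and ocular endpoints should also be measured from Visit 2.* The AHI argument does not establish this. The safety objective concerns chronic NCS use, and 6.4 counts side effects both in the second 9 months and at any time during follow-up.

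It can also be said that naming either starting point would remove the ambiguity, and that a covariate is a separate choice. That is true. The covariate is recommended because the measurement is already being taken and adjustment improves precision under the assumptions shown.

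**Conclusion.** The point holds as an undefined reference for a secondary endpoint, together with an analysis that can be made more efficient without new data. The between-arm expectation (7/hr) and the plan's 97% and 80% powers stand. The affected results are the means by group: in the main scenario with a 4/hr fall in months 0 to 3, the switched-to-placebo mean is +3/hr from month 3 and -1/hr from baseline. That change of sign is conditional and does not occur under the plan's 1/hr scenario, where the mean from baseline is +2/hr. Precision would be lost from baseline only if that SD is larger than the month 3 to month 12 SD, which the plan does not address. The gain from adjustment, 80% to about 88% at effect size 0.597, rests on an assumed correlation of 0.6 and equal variances; over correlations of 0.4 to 0.8 the adjusted power runs from 92% to 84%.

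**What to change.** In 6.2, 6.3.2 and the synopsis, define the 12-month AHI endpoint as AHI at Visit 5 minus AHI at Visit 2. In 6.3.2, and in the matching paragraph of 6.4, state that the two re-randomized arms are compared by a linear model for this change with Visit 2 AHI as covariate, in place of the unadjusted t-test. Report Visit 5 minus baseline by arm as a separate, labelled descriptive result. In 6.4, say that the assumed means and SDs refer to the month 3 to month 12 interval.

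The cost is wording and one model specification. Sleep studies at Visits 2 and 5 are already scheduled, so no visit, measurement or additional child is needed.

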2 STUDY OBJECTIVES

The purpose of the study is to determine the efficacy of NCS vs. placebo in treating OSAS in children.

The primary objective of this study is to determine whether a 3-month course of NCS reduces the AHI in children with OSAS.

The secondary objectives are to:

- To determine which factors modify the response to NCS
- Determine the long-term effect of NCS vs. placebo in the treatment of OSAS in children
- Determine the side-effects associated with chronic NCS use in children with OSAS.

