Side effects of NCS: The proportion of subjects with side-effects will be computed (with 95% CI). The average number of side-effects (with 95% CI) will also be computed. We do not anticipate that there will be an appreciable number of side-effects in either treatment group, but we will have excellent power to detect a meaningful difference between groups. A Fisher's exact test with a 0.050 two-sided significance level will have 84% power to detect the difference between the 50 placebo *vs* 100 NCS subjects at 3 months, if 1% of placebo *vs* 15% of NCS subjects have side-effects at 3 months. For comparison of the 45 treated *vs* 45 placebo subjects during the second 9 months of follow-up, we will have 82% power to detect a difference between 1% *vs* 20% of subjects with side-effects, respectively. In addition, the proportion of the 100 subjects initially randomized to NCS who have side-effects at any time during follow-up will be computed (with 95% CI). An exact binomial test with a nominal 0.050 two-sided significance level will have 85% power to detect an adverse event rate of 6% amongst the 100 NCS subjects at any time during follow-up (*vs* a hypothesized rate of 1%).

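### The two per-period Fisher tests of side-effects have 47% and 21% power at 1% vs 10%; an unconditional exact test does better at almost no cost, and a period-stratified exact test is worth adding as a supplement

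*Combined protocol and SAP*

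**What the plan says.** Section 2 lists this secondary objective: "Determine the side-effects associated with chronic NCS use in children with OSAS". NCS is randomized against placebo twice. The first allocation, at baseline, is 2:1. At 3 months the children first given NCS "will be re-randomized in equal numbers to continued NCS or placebo" (Section 6.4).

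The side-effects paragraph of Section 6.4 plans three tests:

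- **Months 0-3.** Fisher's "exact test with a 0.050 two-sided significance level will have 84% power to detect the difference between the 50 placebo" and the 100 NCS children, "if 1% of placebo *vs* 15% of NCS subjects have side-effects at 3 months".
- **Months 3-12.** With 45 children per re-randomized arm, the plan states: "we will have 82% power to detect a difference between 1% *vs* 20% of subjects with side-effects, respectively". No test is named in this sentence.
- **Single arm.** An exact binomial test against a hypothesized 1%, with "85% power to detect an adverse event rate of 6% amongst the 100 NCS subjects at any time during follow-up".

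The paragraph describes the power for a meaningful group difference as excellent. Section 6.3.4 adds only frequencies and exact binomial confidence intervals. Nothing in the document combines the two randomized contrasts.

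**The concern.** Both randomized comparisons are powered only for very large excesses, 15-fold and 20-fold over a 1% placebo rate. The same paragraph treats 6% against 1% as worth detecting, but only in a test without a control group. For anything between 6% and 15% the document gives no power for a randomized comparison.

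Two features of the plan cost power. Fisher's test conditions on the total number of events, so with groups this small it uses much less than its nominal 5%. And the two randomized contrasts are never brought together. If NCS causes a moderate excess of side-effects, the likely report is two non-significant differences, set beside an overall hypothesis that NCS is safe.

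**Working it through.** **Inputs.** From Section 6.4: 50 placebo vs 100 NCS in months 0-3; 45 vs 45 in months 3-12; two-sided 0.05; placebo rate 1% in both periods; NCS rates 15% and 20%. The 10% and 6% NCS rates and every degree of carry-over are assumptions made here.

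**Step 1: reproduce the plan.** Power = sum over all (x0, x1) of Bin(x0; n0, p0) × Bin(x1; n1, p1) × 1[Fisher p ≤ 0.05], by full enumeration.

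- 50/100, 1% vs 15%: 85.4% (84.5% with a doubled one-sided p-value); stated 84%.
- 45/45, 1% vs 20%: 82.1%; stated 82%. This is why Fisher's test is taken as implied for the second period.
- Single arm, n = 100, reject at 4 or more events: 85.7% at 6%; stated 85%.

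All three agree with the plan.

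**Step 2: true size of Fisher's test.** The largest rejection probability over all common event rates is 4.2% (50/100) and 3.2% (45/45).

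**Step 3: Fisher against Boschloo, within period.** Boschloo's test uses the Fisher p-value as its statistic and raises the cut-off until the maximum size reaches 5%. Its rejection region contains Fisher's, so it is never less powerful.

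| Comparison | Rates | Fisher | Boschloo |
|---|---|---|---|
| 50/100 | 1% vs 15% | 85% | 87% |
| 50/100 | 1% vs 10% | 47% | 55% |
| 45/45 | 1% vs 20% | 82% | 89% |
| 45/45 | 1% vs 15% | 56% | 69% |
| 45/45 | 1% vs 10% | 21% | 35% |

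**Step 4: chance that at least one test is significant, 1% vs 10%, unadjusted, periods independent.** Fisher: 1 − (1 − 0.4746)(1 − 0.2099) = 0.585. Boschloo, from the rounded figures: 1 − (1 − 0.55)(1 − 0.35) = 0.71.

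**Step 5: period-stratified exact test.** The statistic is the total number of NCS events over both periods. Its null distribution, given each period's event total, is the convolution of two hypergeometric distributions. Power is by full enumeration; the last column is Fisher's test on months 0-3 alone.

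| Scenario (placebo 1% in months 0-3) | Stratified | Fisher, months 0-3 |
|---|---|---|
| NCS 10% in both periods, later placebo 1% | 85% | 47% |
| NCS 6% in both periods, later placebo 1% | 41% | 9% |
| NCS 10% in months 0-3 only, 1% in both arms later | 42% | 47% |
| NCS 10%, later placebo 5.5% (half the excess carried over) | 52% | 47% |
| NCS 10%, later placebo 10% (full carry-over) | 25% | 47% |
| Plan's 15% and 20%, full carry-over | 40% | 85% |

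In the first row a doubled one-sided p-value gives 82% instead of 85%. Type I error of the stratified test is 0.65% at a common 1% rate and 3.2% at a common 5% rate, so its power is not bought with inflated size. With a within-child latent correlation of 0.3 or 0.6 between periods, simulated power at 1% vs 10% is 85% and 84%.

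**The case against.** The strongest reply is that the plan contains no error: its power figures reproduce, and separate tests per period are a defensible choice. That stands. The periods answer different questions. Months 0-3 compare starting NCS with never having had it; months 3-12 compare continuing with stopping. They also differ in length. Section 3.1.3 withdraws children with abnormal bone density or eye findings at 3 months, so the re-randomized group is not the group that started. Section 8.11.2 says bone effects of topical steroids usually take many months to years, which argues against equal early and late rates for that outcome.

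A reader might infer that the stratified test should become the main side-effect test, because 85% stands against 47% and 21%. The documents do not support that. Every child on placebo in the second period has had 3 months of NCS, and nothing in the documents rules out carry-over. With full carry-over the stratified test is far weaker than the first-period test alone. The fairer comparator in the favourable case is also 58.5%, not 47% or 21%.

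Nor does the plan ignore moderate harm. The single-arm binomial test spans both periods and has 85% power for 6% vs 1%. But its 1% is fixed, not observed in a concurrent control, so a background rate above 1% could by itself lead to rejection. Section 6.2 also lists knee height, bone, adrenal, ocular and infection outcomes at 12 months, so the safety assessment does not rest on two Fisher tests.

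Conservatism at very low event rates is not peculiar to Fisher's test: at a common 1% rate its size for 50/100 is 0.57%, and that of the stratified test is 0.65%. The case for change rests on power under harm.

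**Conclusion.** This is a loss of efficiency on a stated safety objective, not an arithmetic error. At an assumed 1% vs 10% the planned randomized tests have 47% and 21% power, and 58.5% that either is significant. Replacing Fisher's test by Boschloo's within each period is a gain without a power penalty: 8 points (47% to 55%) and 14 points (21% to 35%) at that alternative, and 2 and 7 points at the plan's own rates.

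The stratified test has a further advantage only when the excess is present in both periods and little of it carries over: about 85% at 1% vs 10% and 41% at 1% vs 6%. Otherwise it gains little or loses, which fits a supplementary role. These conclusions rest on the plan's 1% placebo rate, on Fisher's test being intended for the second period, and on the assumed NCS rates and carry-over.

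**What to change.** In Sections 6.4 and 6.3.4:

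1. Keep the two per-period comparisons, name the test for each, and make it Boschloo's unconditional exact test. State power at a moderate excess (55% and 35% at 1% vs 10%) next to the present figures (87% at 1% vs 15%; 89% at 1% vs 20%).
2. Prespecify, as supplementary, an exact test stratified by period of no NCS effect on side-effects. Use the initial arm for months 0-3 and the re-randomized arm for months 3-12, and count events that start in each period. Report the per-period estimates with confidence intervals whatever it shows.
3. State its limits: about 85% (1% vs 10%) and 41% (1% vs 6%) with equal rates and no carry-over; at 10%, about 42% if harm is confined to months 0-3, 52% with half carry-over and 25% with full carry-over.
4. Say that the single-arm binomial test has no concurrent control.

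The cost is wording and one more analysis of data already collected. Recruitment, visits and treatment do not change. The analyst should confirm that the software named in the synopsis can run both exact tests.
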